13.1 Table Conventions

- If the categories of a parameter are ordered, then all categories between the maximum and minimum category are presented in the table even in case of frequency equal to 0.
- If the categories are not ordered (e.g., Medical History), then only those categories for which there is at least 1 subject represented in 1 or more groups are included.
- Unless otherwise specified, the estimated mean and median for a set of values are printed out to 1 more significant digit than the original values, and standard deviations.
- Missing descriptive statistics or p-values which cannot be estimated are reported as “-”.

15.1 Tables

Number	Title	Population	KFR	Final Analysis
Table 14.1.1	Subject enrolment and disposition	ENR	X	X
Table 14.1.2.1	Major protocol deviations	RND		X
Table 14.1.2.2	Minor protocol deviations	RND		X
Table 14.1.3.1	Study discontinuation	RND		X
Table 14.1.4.1	Summary of demographics characteristics	FAS	X	X
Table 14.1.4.2	Summary of baseline characteristics	FAS	X	X
Table 14.1.5.1	Medical History	FAS		X
Table 14.1.5.2	Concomitant diseases	FAS		X
Table 14.1.6.1	Prior medication	FAS		X
Table 14.1.6.2	Concomitant medication	FAS		X
Table 14.1.6.3	Prior medication	SAF		X
Table 14.1.6.4	Concomitant medication	SAF		X
Table 14.1.7	Dry Eye History	FAS		X
Table 14.1.8.1	Other baseline characteristics: Eligible eye, SANDE scores, IDEEL scores, Schirmer test I and Schirmer test II	FAS		X
Table 14.1.8.2	Other baseline characteristics by eye: BCDVA, External ocular examination, Slit Lamp Ophthalmic Exam, NEI scale and TFBUT	FAS		X
Table 14.2.1.1	Schirmer I test (without anesthesia) >10mm/5min at week 4 - Logistic regression model - Multiple imputation	FAS	X	X
Table 14.2.1.2	Change from baseline in the global SANDE score at week 12 - Analysis of Covariance (ANCOVA) - Multiple imputation	FAS	X	X
Table 14.2.2.1	Sensitivity analysis: Schirmer I test (without anesthesia) >10mm/5min at week 4 - Logistic regression model - Multiple imputation	FAS		X
Table 14.2.2.2	Sensitivity analysis: Change from baseline in the global SANDE score at week 12 - Analysis of Covariance (ANCOVA) - Multiple imputation	FAS		X
Table 14.2.2.3	Sensitivity analysis: Schirmer I test (without anesthesia) >10mm/5min at week 4 - Logistic regression model - Tipping point	FAS		X
Table 14.2.2.4	Sensitivity analysis: Change from baseline in the global SANDE score at week 12 - Analysis of Covariance (ANCOVA) - Tipping point	FAS		X

Number	Title	Population	KFR	Final Analysis
Table 14.2.3.1	Supportive analysis: Schirmer I test (without anesthesia) >10mm/5min at week 4 - Logistic regression model - Complete cases only	FAS		X
Table 14.2.3.2	Supportive analysis: Change from baseline in the global SANDE score at week 12 - Analysis of Covariance (ANCOVA) - Complete cases only	FAS		X
Table 14.2.3.3	Supportive analysis: Schirmer I test (without anesthesia) >10mm/5min at week 4 - Logistic regression model - Multiple imputation	PP		X
Table 14.2.3.4	Supportive analysis: Change from baseline in the global SANDE score at week 12 - Analysis of Covariance (ANCOVA) - Multiple imputation	PP		X
Table 14.2.4.1	Schirmer I test (without anesthesia) >10mm/5min at week 8 - Logistic regression model - Multiple imputation	FAS		X
Table 14.2.4.2	Change from baseline in SANDE scores for severity at week 12. - Analysis of Covariance (ANCOVA) - Multiple imputation	FAS		X
Table 14.2.4.3	Change from baseline in SANDE scores for frequency at week 12. - Analysis of Covariance (ANCOVA) - Multiple imputation	FAS		X
Table 14.2.4.4.1.1	Change from baseline in IDEEL Quality of Life module (Daily activities) up to week 12 - MMRM - Multiple imputation	FAS		X
Table 14.2.4.4.1.2	Change from baseline in IDEEL Quality of Life module (Feelings) up to week 12 - MMRM - Multiple imputation	FAS		X
Table 14.2.4.4.1.3	Change from baseline in IDEEL Quality of Life module (Work) up to week 12 - MMRM - Multiple imputation	FAS		X
Table 14.2.4.4.2.1	Change from baseline in Dry eye Treatment satisfaction & Bother module (Treatment – In General) up to week 12 - MMRM - Multiple imputation	FAS		X
Table 14.2.4.4.2.1	Change from baseline in Dry eye Treatment satisfaction & Bother module (Treatment – Eye drops) up to week 12 - MMRM - Multiple imputation	FAS		X
Table 14.2.4.4.3	Change from baseline in IDEEL Dry eye Symptom bother module up to week 12 - MMRM - Multiple imputation	FAS		X
Table 14.2.4.5	Change from baseline in Cornea and conjunctiva vital staining with fluorescein NEI scale up to week 12 - MMRM - Multiple imputation	FAS		X
Table 14.2.4.6	Change from baseline in TFBUT up to week 12 - MMRM - Multiple imputation	FAS		X
Table 14.2.5.1	Absolute values and change from baseline in Schirmer I test at each timepoint.	FAS	X	X
Table 14.2.5.2.1	Absolute values and change from baseline in SANDE global scores at each timepoint.	FAS	X	X
Table 14.2.5.2.2	Absolute values and change from baseline in SANDE severity scores at each timepoint.	FAS	X	X
Table 14.2.5.2.3	Absolute values and change from baseline in SANDE frequency scores at each timepoint.	FAS	X	X
Table 14.2.5.3	Number of patients experienced a worsening in symptom scores (SANDE global score) and/or NEI score $\geq 50\%$ assessed at week 4	FAS		X

Number	Title	Population	KFR	Final Analysis
Table 14.2.5.4.1	Absolute values and change from baseline in IDEEL Quality of Life module at each timepoint.	FAS	X	X
Table 14.2.5.4.2	Absolute values and change from baseline in IDEEL Dry eye Treatment satisfaction & Bother module at each timepoint.	FAS	X	X
Table 14.2.5.4.3	Absolute values and change from baseline in IDEEL Dry eye Symptom bother module at each timepoint.	FAS	X	X
Table 14.2.5.5	Absolute values and change from baseline in Cornea and conjunctiva vital staining with fluorescein (NEI scale) at each timepoint.	FAS	X	X
Table 14.2.5.6	Absolute values and change from baseline in TFBUT at each timepoint.	FAS	X	X
Table 14.2.6.1.1	Subgroup evaluation: Schirmer I test (without anesthesia) >10mm/5min at week 4 - Treatment by region interaction. Logistic regression model - Multiple imputation	FAS		X
Table 14.2.6.1.2	Subgroup evaluation: Schirmer I test (without anesthesia) >10mm/5min at week 4 - Treatment by Sjögren's syndrome interaction. Logistic regression model - Multiple imputation	FAS		X
Table 14.2.6.1.3	Subgroup evaluation: Schirmer I test (without anesthesia) >10mm/5min at week 4 - Treatment by medical history interaction. Logistic regression model - Multiple imputation	FAS		X
Table 14.2.6.1.4	Subgroup evaluation: Schirmer I test (without anesthesia) >10mm/5min at week 4 - Treatment by concomitant medication interaction. Logistic regression model - Multiple imputation	FAS		X
Table 14.2.6.2.1	Subgroup evaluation: Change from baseline in the global SANDE score at week 12 - Treatment by region interaction. Analysis of Covariance (ANCOVA) - Multiple imputation	FAS		X
Table 14.2.6.2.2	Subgroup evaluation: Change from baseline in the global SANDE score at week 12 - Treatment by sjögren's syndrome interaction. Analysis of Covariance (ANCOVA) - Multiple imputation	FAS		X
Table 14.2.6.2.3	Subgroup evaluation: Change from baseline in the global SANDE score at week 12 - Treatment by medical history interaction. Analysis of Covariance (ANCOVA) - Multiple imputation	FAS		X
Table 14.2.6.2.4	Subgroup evaluation: Change from baseline in the global SANDE score at week 12 - Treatment by concomitant medication interaction. Analysis of Covariance (ANCOVA) - Multiple imputation	FAS		X
Table 14.2.6.3.1	Absolute values and change from baseline in Schirmer I test at each timepoint by age class.	FAS		X
Table 14.2.6.3.2	Absolute values and change from baseline in Schirmer I test at each timepoint by race.	FAS		X
Table 14.2.6.3.3	Absolute values and change from baseline in Schirmer I test at each timepoint by ethnicity.	FAS		X

Number	Title	Population	KFR	Final Analysis
Table 14.2.6.3.4	Absolute values and change from baseline in Schirmer I test at each timepoint by gender.	FAS		X
Table 14.2.6.4.1	Absolute values and change from baseline in Cornea and conjunctiva vital staining with fluorescein (NEI scale) at each timepoint by age class.	FAS		X
Table 14.2.6.4.2	Absolute values and change from baseline in Cornea and conjunctiva vital staining with fluorescein (NEI scale) at each timepoint by race.	FAS		X
Table 14.2.6.4.3	Absolute values and change from baseline in Cornea and conjunctiva vital staining with fluorescein (NEI scale) at each timepoint by ethnicity.	FAS		X
Table 14.2.6.4.4	Absolute values and change from baseline in Cornea and conjunctiva vital staining with fluorescein (NEI scale) at each timepoint by gender.	FAS		X
Table 14.2.6.5.1	Absolute values and change from baseline in TFBUT at each timepoint by age class.	FAS		X
Table 14.2.6.5.2	Absolute values and change from baseline in TFBUT at each timepoint by race.	FAS		X
Table 14.2.6.5.3	Absolute values and change from baseline in TFBUT at each timepoint by ethnicity.	FAS		X
Table 14.2.6.5.4	Absolute values and change from baseline in TFBUT at each timepoint by gender.	FAS		X
Table 14.2.6.6.1.1	Absolute values and change from baseline in SANDE global scores at each timepoint by age class.	FAS		X
Table 14.2.6.6.1.2	Absolute values and change from baseline in SANDE global scores at each timepoint by race.	FAS		X
Table 14.2.6.6.1.3	Absolute values and change from baseline in SANDE global scores at each timepoint by ethnicity.	FAS		X
Table 14.2.6.6.1.4	Absolute values and change from baseline in SANDE global scores at each timepoint by gender.	FAS		X
Table 14.2.6.6.2.1	Absolute values and change from baseline in SANDE severity scores at each timepoint by age class.	FAS		X
Table 14.2.6.6.2.2	Absolute values and change from baseline in SANDE severity scores at each timepoint by race.	FAS		X
Table 14.2.6.6.2.3	Absolute values and change from baseline in SANDE severity scores at each timepoint by ethnicity.	FAS		X
Table 14.2.6.6.2.4	Absolute values and change from baseline in SANDE severity scores at each timepoint by gender.	FAS		X
Table 14.2.6.6.3.1	Absolute values and change from baseline in SANDE frequency scores at each timepoint by age class.	FAS		X
Table 14.2.6.6.3.2	Absolute values and change from baseline in SANDE frequency scores at each timepoint by race.	FAS		X
Table 14.2.6.6.3.3	Absolute values and change from baseline in SANDE frequency scores at each timepoint by ethnicity.	FAS		X
Table 14.2.6.6.3.4	Absolute values and change from baseline in SANDE frequency scores at each timepoint by gender.	FAS		X

Number	Title	Population	KFR	Final Analysis
Table 14.2.6.7.1.1	Absolute values and change from baseline in IDEEL Quality of Life module at each timepoint by age class.	FAS		X
Table 14.2.6.7.1.2	Absolute values and change from baseline in IDEEL Quality of Life module at each timepoint by race.	FAS		X
Table 14.2.6.7.1.3	Absolute values and change from baseline in IDEEL Quality of Life module at each timepoint by ethnicity.	FAS		X
Table 14.2.6.7.1.4	Absolute values and change from baseline in IDEEL Quality of Life module at each timepoint by gender.	FAS		X
Table 14.2.6.7.2.1	Absolute values and change from baseline in IDEEL Dry eye Treatment satisfaction & Bother module at each timepoint by age class.	FAS		X
Table 14.2.6.7.2.2	Absolute values and change from baseline in IDEEL Dry eye Treatment satisfaction & Bother module at each timepoint by race.	FAS		X
Table 14.2.6.7.2.3	Absolute values and change from baseline in IDEEL Dry eye Treatment satisfaction & Bother module at each timepoint by ethnicity.	FAS		X
Table 14.2.6.7.2.4	Absolute values and change from baseline in IDEEL Dry eye Treatment satisfaction & Bother module at each timepoint by gender.	FAS		X
Table 14.2.6.7.3.1	Absolute values and change from baseline in IDEEL Dry eye Symptom bother module at each timepoint by age class.	FAS		X
Table 14.2.6.7.3.2	Absolute values and change from baseline in IDEEL Dry eye Symptom bother module at each timepoint by race.	FAS		X
Table 14.2.6.7.3.3	Absolute values and change from baseline in IDEEL Dry eye Symptom bother module at each timepoint by ethnicity.	FAS		X
Table 14.2.6.7.3.4	Absolute values and change from baseline in IDEEL Dry eye Symptom bother module at each timepoint by gender.	FAS		X
Table 14.2.6.3.x Table 14.2.6.7.3.x (x can vary from 5 to 8, based on how many subgroups will be used)	Repeat set of tables from 14.2.6.3.1 to 14.2.6.2.7.3.1 for all subgroups defined in the SAP (section 7.5), in case the interaction is statistically significant in the model specified before (i.e. 14.2.6.1.1)	FAS		X
Table 14.3.1.1	Summary of treatment emergent adverse events (TEAEs)	SAF		X
Table 14.3.1.2	Summary of Ophthalmic TEAEs by primary SOC and PT and by study period	SAF		X
Table 14.3.1.3	Summary of Non-Ophthalmic TEAEs by primary SOC and PT and by study period	SAF		X
Table 14.3.1.4	Summary of TEAEs by primary SOC, PT and Severity	SAF		X
Table 14.3.1.5	Summary of Serious TEAEs by Primary SOC and PT and by study period	SAF		X
Table 14.3.1.6	Summary of ADRs by Primary SOC and PT and by study period	SAF		X
Table 14.3.1.7	Summary of ADRs by Primary SOC and PT and Severity	SAF		X

Number	Title	Population	KFR	Final Analysis
Table 14.3.1.8	Summary of TEAEs leading to IMP Discontinuation by Primary SOC and PT and by study period	SAF		X
Table 14.3.1.9	Summary of TEAEs leading to study Discontinuation by Primary SOC and PT and by study period	SAF		X
Table 14.3.1.10	Summary of TEAEs leading to Death by Primary SOC and PT	SAF		X
Table 14.3.2.1.1	Compliance to IMP	FAS		X
Table 14.3.2.1.2	Compliance to IMP	SAF		X
Table 14.3.2.2.1	Extent of exposure to IMP	FAS		X
Table 14.3.2.2.2	Extent of exposure to IMP	SAF		X
Table 14.3.2.3.1	Use of preservative free artificial tears by study period	FAS		X
Table 14.3.2.3.2	Use of preservative free artificial tears by study period	SAF		X

15.2 Listings

Number	Title	Population	KFR	Final analysis
Listing 16.1.7	Randomisation Scheme	RND		X
Listing 16.2.1	Patient disposition in analysis data sets and primary reasons for withdrawal	ENR		X
Listing 16.2.2	Protocol deviations	RND		X
Listing 16.2.3.1	Study discontinuation and reasons for withdrawal	RND		X
Listing 16.2.3.2	Study Visits	RND		X
Listing 16.2.4.1	Demographic data	SAF		X
Listing 16.2.4.2	Baseline Characteristics	SAF		X
Listing 16.2.4.3	Medical history	SAF		X
Listing 16.2.4.4	Concomitant Diseases	SAF		X
Listing 16.2.4.5	Prior medication and therapy	SAF		X
Listing 16.2.4.6	Concomitant medication and therapy	SAF		X
Listing 16.2.4.7	Dry Eye History	SAF		X
Listing 16.2.6.1	Schirmer test I by patient and visit	SAF		X
Listing 16.2.6.2	Schirmer test II by patient and visit	SAF		X
Listing 16.2.6.3	SANDE scores by patient and visit	SAF		X
Listing 16.2.6.4	NEI scale by patient and visit	SAF		X
Listing 16.2.6.5	TFBUT by patient and visit	SAF		X
Listing 16.2.6.6	IDEEL scores by patient and visit	SAF		X
Listing 16.2.7.1	Listing of all AEs by Patient	SAF		X
Listing 16.2.7.2	Listing of all AEs leading to IMP discontinuation	SAF		X
Listing 16.2.7.3	Listing of all AEs leading to study discontinuation	SAF		X
Listing 16.2.7.4	Listing of SAEs by Patient	SAF		X
Listing 16.2.7.5	Listing of ADR by Patient	SAF		X
Listing 16.2.7.6	Listing of Deaths.	SAF		X
Listing 16.2.5.1	Compliance to IMP	SAF		X
Listing 16.2.5.2	Exposure to IMP	SAF		X
Listing 16.2.5.3	Use of preservative free artificial tears	SAF		X

15.3 Figures

Number	Title	Population	KFR	Final analysis
Figure 14.1.3.2	Time from randomization to discontinuation (Kaplan-Meier)	RND		X
Figure 14.2.3.5	Tipping point Schirmer test	FAS		X
Figure 14.2.3.6	Tipping point plot SANDE	FAS		X
Figure 14.2.5.1.1	Schirmer I test Observed Mean (\pm SEM) at each timepoint.	FAS		X
Figure 14.2.5.1.2	Schirmer I test Mean change from baseline (\pm SEM) at each timepoint.	FAS		X
Figure 14.2.5.1.3	Observed percentage of patients with Schirmer I test >10 mm/5min at each timepoint.	FAS		X
Figure 14.2.5.2.1.1	SANDE global score Observed Mean (\pm SEM) at each timepoint.	FAS		X
Figure 14.2.5.2.1.2	SANDE global score Mean change from baseline (\pm SEM) at each timepoint.	FAS		X
Figure 14.2.5.5.1	Cornea and conjunctiva vital staining total score Observed Mean (\pm SEM) at each timepoint.	FAS		X
Figure 14.2.5.5.2	Cornea and conjunctiva vital staining total score Mean change from baseline (\pm SEM) at each timepoint.	FAS		X
Figure 14.2.5.6.1	TFBUT Observed Mean (\pm SEM) at each timepoint.	FAS		X
Figure 14.2.5.6.2	TFBUT Mean change from baseline (\pm SEM) at each timepoint.	FAS		X

15.5 SAS Code for the primary analysis

15.5.1 Schirmer I test >10mm/5min at week 4

Standard	Alternative code in case of no convergence
<pre> PROC MI DATA= EFFICACY01 NIMPUTE=200 SEED=820520 OUT=EFFICACY_MONO1; VAR BASVAL SCHIRMER_W2 AVAL; MCMC CHAIN=SINGLE NBITER=200 NITER=100 IMPUTE=MONOTONE; WHERE TRT=1; RUN; PROC MI DATA=EFFICACY01 NIMPUTE=200 SEED=820520 OUT=EFFICACY_MONO2; VAR BASVAL SCHIRMER_W2 AVAL; MCMC CHAIN=SINGLE NBITER=200 NITER=100 IMPUTE=MONOTONE; WHERE TRT=2; RUN; DATA EFFICACY_MONO; SET EFFICACY_MONO1 EFFICACY_MONO2; RUN; </pre>	<pre> PROC MI DATA= EFFICACY01 NIMPUTE=200 SEED=820520 OUT=EFFICACY_MONO; VAR BASVAL TRT SCHIRMER_W2 AVAL; MCMC CHAIN=SINGLE NBITER=200 NITER=100 IMPUTE=MONOTONE; RUN; </pre>
<pre> PROC SORT; BY _IMPUTATION_ SUBJID; RUN; </pre>	
<pre> PROC MI DATA=EFFICACY_MONO SEED=200582 NIMPUTE=1 OUT=EFFICACY_IMP; BY _IMPUTATION_; CLASS TRT AGE SEX EOTSTT; MONOTONE REG(AVAL = TRT AGE SEX BASVAL / DETAILS); MNAR MODEL(AVAL / MODELOBS= (EOTSTT='NOT COMPLETED')); VAR TRT AGE SEX BASVAL SCHIRMER_W2 AVAL; RUN; </pre>	<pre> PROC MI DATA=EFFICACY_MONO SEED=200582 NIMPUTE=1 OUT=EFFICACY_IMP; BY _IMPUTATION_; CLASS TRT AGE SEX EOTSTT; MONOTONE REG(AVAL = TRT AGE SEX BASVAL / DETAILS); MNAR MODEL(AVAL / MODELOBS= (TRT=2 /*Vehicle*/)); VAR TRT AGE SEX BASVAL SCHIRMER_W2 AVAL; RUN; </pre>

Standard	Alternative code in case of no convergence
<pre> DATA EFFICACY_IMP; SET EFFICACY_IMP; IF AVAL>10 THEN AVALC='Y'; ELSE AVALC='N'; RUN; ODS OUTPUT DIFFS=GLIMMIX_DIFFS; ODS OUTPUT PARAMETERESTIMATES=ESTIMATES; PROC GLIMMIX DATA=EFFICACY_IMP METHOD = QUAD; BY _IMPUTATION_; CLASS TRT(REF="1") AGE(REF="<=XX") SEX(REF="F") SITEID; MODEL AVALC(EVENT='Y')=TRT AGE SEX BASVAL /S DIST=BINARY LINK=LOGIT OR; RANDOM INTERCEPT / SUBJECT=SITEID; LSMEANS TRT / ILINK ODDSRATIO CL DIFF; RUN; ODS OUTPUT PARAMETERESTIMATES=POOLED_ESTIMATES; PROC MIANALYZE PARMS = ESTIMATES ; CLASS TRT AGE SEX; MODELEFFECTS INTERCEPT TRT AGE SEX BASVAL ; RUN; ODS OUTPUT PARAMETERESTIMATES=POOLED_DIFFS; PROC MIANALYZE DATA = GLIMMIX_DIFFS ; MODELEFFECTS ESTIMATE; STDERR STDERR; RUN; DATA POOLED_ODDS_RATIO; SET POOLED_DIFFS; ODDSRATIO=EXP(ESTIMATE); ODDS_95LL=EXP(LCLMEAN); ODDS_95UL=EXP(UCLMEAN); RUN; </pre>	

15.5.2 Change from baseline in the global SANDE score at week 12

Standard	Alternative code in case of no convergence
<pre> PROC MI DATA= EFFICACY01 NIMPUTE=200 SEED=37103939 OUT=EFFICACY_MONO1; VAR BASVAL SANDE_W2 SANDE_W4 SANDE_W8 AVAL; MCMC CHAIN=SINGLE NBITER=200 NITER=100 IMPUTE=MONOTONE; WHERE TRT=1; RUN; PROC MI DATA=EFFICACY01 NIMPUTE=200 SEED=37103939 OUT=EFFICACY_MONO2; VAR BASVAL SANDE_W2 SANDE_W4 SANDE_W8 AVAL; MCMC CHAIN=SINGLE NBITER=200 NITER=100 IMPUTE=MONOTONE; WHERE TRT=2; RUN; DATA EFFICACY_MONO; SET EFFICACY_MONO1 EFFICACY_MONO2; RUN; </pre>	<pre> PROC MI DATA= EFFICACY01 NIMPUTE=200 SEED=37103939 OUT=EFFICACY_MONO; VAR BASVAL TRT SANDE_W2 SANDE_W4 SANDE_W8 AVAL; MCMC CHAIN=SINGLE NBITER=200 NITER=100 IMPUTE=MONOTONE; RUN; </pre>
<pre> PROC SORT; BY _IMPUTATION_ SUBJID; RUN; </pre>	
<pre> PROC MI DATA=EFFICACY_MONO SEED=200582 NIMPUTE=1 OUT=EFFICACY_IMP; BY _IMPUTATION_; CLASS TRT AGE SEX EOTSTT; MONOTONE REG(AVAL = TRT AGE SEX / DETAILS); MNAR MODEL(AVAL / MODELOBS= (EOTSTT='NOT COMPLETED')); VAR TRT AGE SEX BASVAL SANDE_W2 SANDE_W4 SANDE_W8 AVAL; RUN; </pre>	<pre> PROC MI DATA=EFFICACY_MONO SEED=200582 NIMPUTE=1 OUT=EFFICACY_IMP; BY _IMPUTATION_; CLASS TRT AGE SEX EOTSTT; MONOTONE REG(AVAL = TRT AGE SEX / DETAILS); MNAR MODEL(AVAL / MODELOBS= (TRT=2 /*Vehicle*/)); VAR TRT AGE SEX BASVAL SANDE_W2 SANDE_W4 SANDE_W8 AVAL; RUN; </pre>

Standard	Alternative code in case of no convergence
<pre>ODS OUTPUT DIFFS=DIFFS; ODS OUTPUT PARAMETERESTIMATES=ESTIMATES; PROC MIXED DATA=EFFICACY_IMP; BY _IMPUTATION_; CLASS TRT(REF="1") SEXC(REF="F") SITEID; MODEL AVAL=TRT AGE SEXC BASVAL /S; RANDOM INTERCEPT / SUBJECT=SITEID; LSMEANS TRT / CL DIFF; RUN; ODS OUTPUT PARAMETERESTIMATES=POOLED_ESTIMATES; PROC MIANALYZE PARMS = ESTIMATES ; CLASS TRT SEXC; MODELEFFECTS INTERCEPT TRT AGE SEXC BASVAL ; RUN; ODS OUTPUT PARAMETERESTIMATES=POOLED_DIFFS; PROC MIANALYZE DATA = DIFFS ; MODELEFFECTS ESTIMATE; STDERR STDERR; RUN;</pre>

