- The remaining missing values in the vehicle group with a monotone missing data pattern will be imputed based on observed data of the control patients with available endpoint, while the remaining missing values in the treatment group with a monotone missing data pattern will be imputed based on observed and imputed data of the control patients;
- All imputed data will be pooled and analyzed, and results will be combined using Rubin's to draw inference.

Whether for MI-RD or wash-out approach, the adjusted estimated treatment differences between cenegermin and vehicle (difference in proportions for Schirmer's test and differences in means for SANDE) will be displayed together with the corresponding two-side 95% confidence intervals and p-values.

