7.3 Primary estimand

The primary endpoints will be analyzed using treatment policy estimands, defined by the following:

Primary endpoint:

- Population: Subjects in the FAS population.
- Variable: Schirmer I test at week 4.
- Intercurrent event: The occurrence of an intercurrent event is irrelevant. All observed values will be used regardless of occurrence of an intercurrent event. Retrieved dropouts will be used for data imputation of missing data.
- Population-level summary: difference in proportion of patients reaching a value of Schirmer I test (without anesthesia) >10mm/5min at week 4.

Coprimary endpoint:

- Population: Subjects in the FAS population.
- Variable: SANDE global score at week 12.
- Intercurrent event: The occurrence of an intercurrent event is irrelevant. All observed values will be used regardless of occurrence of an intercurrent event. Retrieved dropouts will be used for data imputation of missing data.
- Population-level summary: difference in change from baseline in the global SANDE score at week 12.

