10.1.2 Analysis details

Both co-primary endpoints will be analysed by means of MI-RD to handle missing data. Retrieved drop-out patients are defined as patients who discontinue study treatment and decide to remain in the study by following the schedule of assessments and continuing to adhere to protocol requirements. Consequently, for each primary endpoint, MI will be performed based on the subjects' allocated treatment arm and observed values (baseline and intermediate) as covariates in a regression model using data from Retrieved drop-out patients that have the primary endpoint assessment done.

10.1.2.1 Schirmer I test $>10\text{mm}/5\text{min}$ at week 4

This primary endpoint will be analyzed by means of a logistic regression model adjusting by pre-defined baseline factors (gender, age class, baseline Schirmer I test value as fixed effects and site as random effect) and a one-sided test will be used to test for differences between treatment groups.

For the imputation of missing data of Schirmer I test, a regression model will be created by including the baseline Schirmer I test value, gender, age class, and Schirmer I test at week 2. Two hundred data sets will be generated, and the random seed number will be 820520. MI will be implemented in the following steps:

1. Partial imputation assuming Missing at Random (MAR) will be carried out to impute intermittent (non-monotone) missing data of Schirmer I test up to week 4 based on a

multivariate joint Gaussian imputation model using the Markov chain Monte Carlo (MCMC) method. A separate imputation model will be used for each treatment arm. In case of non-convergence or non-estimability issues, a single imputation model will be considered (with treatment arm added as explanatory variable to the model). A total of 200 datasets will be created. These datasets will be utilized in Step #2.

2. The remaining monotone missing data will be imputed using a MI regression including the same explanatory variables of the previous step. According to MI-RD approach, only non-missing values from retrieve dropouts will be used to inform the regression model.
3. Each of the 200 imputed datasets will be analyzed using observed and imputed data. Rubin's rule will be used for combining results to draw inference.

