If there are not enough retrieved dropouts for convergence of MI-RD regression model, a reference-based Multiple Imputation (MI) approach will be adopted to consider a missing not at random (MNAR) mechanism for missing data: imputation of values in the rhNGF arm (above step #2) will be done using the non-missing values from the control group (this approach will be referred as "Copy Reference"). This approach does not assume benefits for rhNGF in case of discontinuation and limits a post-discontinuation clinical effect to that of vehicle. The final decision on the use of the MI-RD vs Copy-Reference for this endpoint will be done at the time of the analysis and reported in the CSR.

Whether for MI-RD or Copy-Reference approach, the adjusted estimated treatment differences in proportions between cenegegermin and vehicle at week 4 will be displayed together with the corresponding two-side 95% confidence intervals and p-value.

10.1.2.2 Change from baseline in the global SANDE score at week 12

This co-primary endpoint will be analyzed by means of an Analysis of Covariance (ANCOVA) adjusting by pre-defined baseline factors (gender, age class, baseline global SANDE score as fixed effects and site as random effect) and a one-sided test will be used to test for differences between treatment groups. Rules for derivation of SANDE scores are reported in section 12.2.

For the imputation of missing data, a regression model will be created by including the baseline global SANDE score, gender, age class, and intermediate global SANDE scores up to week 12. Two hundred data sets will be generated, and the random seed number will be 37103939. MI will be implemented in the following steps:

1. Partial imputation assuming MAR will be carried out to impute intermittent (non-monotone) missing data of global SANDE score based on a multivariate joint Gaussian imputation model using the MCMC method. A separate imputation model will be used for each treatment arm. In case of non-convergence or non-estimability issues, a single imputation model will be considered (with treatment arm added as explanatory variable to the model). A total of 200 datasets will be created. These datasets will be utilized in Step #2.
2. The remaining monotone missing data will be imputed using a MI regression including the same explanatory variables of the previous step. According to MI-RD approach, only non-missing values from retrieve dropouts will be used to inform the regression model.

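### The Schirmer co-primary effect is declared as a difference in proportions, but the SAP's primary code yields only an odds ratio and the SAP names no method for the difference

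*SAP*

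**What the plan says.** **Declared effect.** SAP 7.3 gives, for the first co-primary: "Population-level summary: difference in proportion of patients reaching a value of Schirmer I test (without anesthesia) >10mm/5min at week 4". SAP 10.1.2.1 then promises "the adjusted estimated treatment differences in proportions between" the two arms at week 4, with a two-sided 95% CI and a p-value. Protocol 9.4.3.1 makes the same commitment ("difference in proportions for Schirmer's test and differences in means for SANDE) will be displayed"). SAP 10.1.3 repeats it for the missing-at-random sensitivity analysis.

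**Declared model.** SAP 10.1.2.1: "This primary endpoint will be analyzed by means of a logistic regression model adjusting by pre-defined baseline factors". Gender, age class and baseline Schirmer value are fixed effects, site is random, and the test is one-sided.

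**Code.** SAP 15.5.1 fits this model with a logit link ("MODEL AVALC(EVENT='Y')=TRT AGE SEX BASVAL /S DIST=BINARY LINK=LOGIT OR") and requests "LSMEANS TRT / ILINK ODDSRATIO CL DIFF". It keeps two output tables: "ODS OUTPUT DIFFS=GLIMMIX_DIFFS; ODS OUTPUT PARAMETERESTIMATES=ESTIMATES". Both are pooled with MIANALYZE, and the pooled treatment difference is then exponentiated: "DATA POOLED_ODDS_RATIO; SET POOLED_DIFFS; ODDSRATIO=EXP(ESTIMATE); ODDS_95LL=EXP(LCLMEAN".

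**Changes list.** SAP 7.9, which sets out departures from the protocol, does not mention a move to an odds ratio.

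**The concern.** The estimand section, the results text and the protocol all use the risk-difference scale. The only worked specification of the analysis ends on a different scale. A programmer who follows the appendix delivers an odds ratio that none of the three declares. A programmer who follows the text has to choose the estimator, the standard error and the pooling step for a co-primary effect.

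That choice could fall after unblinding, because SAP 6.2 places the analyses after the single lock and unblinding. The table concerned (14.2.1.1) is among the key first results in SAP 15.1, so it would be one of the first efficacy results released.

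**Working it through.** **Inputs.** SAP section 5: vehicle responder rate 5%, difference 30 points (so 35% on cenegermin), 1:1 allocation, 90 evaluable patients (45 per arm), one-sided alpha 0.025, stated Schirmer power 95.8%. The calculations below use no covariates and no site effect.

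**1. The plan's own figure.** Pooled test of two proportions, mean rate 0.20:
- SE under the null = √(2 × 0.20 × 0.80 / 45) = 0.0843
- SE under the alternative = √((0.35 × 0.65 + 0.05 × 0.95) / 45) = 0.0782
- Power = Φ((0.30 − 1.96 × 0.0843) / 0.0782) = 95.76%

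This matches the stated 95.8%, so the sample size was set on the same risk-difference scale as the estimand.

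**2. The declared effect at the planning rates.** Difference = 0.30, SE 0.078, 95% CI 0.30 ± 1.96 × 0.078, about 0.147 to 0.453.

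**3. What the code returns at the same rates** (taken as cenegermin over vehicle).
- Odds ratio = (0.35/0.65) / (0.05/0.95) = 10.23; log odds ratio 2.325
- SE = √(1/(45 × 0.35 × 0.65) + 1/(45 × 0.05 × 0.95)) = 0.752
- 95% CI = exp(2.325 ± 1.96 × 0.752), about 2.3 to 44.7

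**4. Can the difference be recovered from the odds ratio?** Only if an arm-level rate is also known. With vehicle rate p0 and odds ratio 10.23, the cenegermin rate is 10.23·o/(1 + 10.23·o), where o = p0/(1 − p0). Vehicle rates other than 5% are assumed, to show the range:

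| Vehicle rate | Cenegermin rate | Difference (points) |
|---|---|---|
| 2% | 17.3% | 15.3 |
| 5% | 35.0% | 30.0 |
| 10% | 53.2% | 43.2 |
| 15% | 64.4% | 49.4 |
| 20% | 71.9% | 51.9 |

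**5. Does any other step in the code supply the difference?** No. The saved differences and parameter estimates are both on the log-odds scale. ILINK asks for back-transformed arm probabilities, but the least-squares-means table that holds them is neither saved nor pooled.

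**6. Does the mismatch affect the test?** With no treatment effect the log odds ratio and the risk difference are both zero, so the logistic treatment test addresses H01 whichever measure is reported.

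**The case against.** The strongest reply is that the appendix is sample code. The governing text still commits to the difference in proportions with its CI, and the title of Table 14.2.1.1 does not restrict the output to an odds ratio. This stands in part. A reader might infer that the declared effect will never be estimated, and the documents do not support that. They show that the supplied code does not produce it and that no method is named. That is still a contradiction within the plan: the appendix is titled as the code for the primary analysis, fixes seeds, imputations and pooling, and ends on a measure that the estimand does not mention.

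Two other strong readings do not hold.

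- **A biased risk difference from subtracting the ILINK means.** Such means would weight sex and age class equally and set the site effect to zero. Assuming 90% women, an age log odds ratio of 0.5 and a male log odds ratio of −1, 0 or +1, their difference would be 22.8, 29.9 or 37.3 points against a FAS difference of 30. But neither document plans this subtraction, and none of those inputs is in the documents. The figures are a reason to name the method, not a measure of error in this plan.
- **A p-value that does not belong to the reported effect.** SAP 10.1.2.1 attaches the one-sided test to the logistic model, SAP 10.1.1 rejects H01 on the primary analysis p-value, and SAP 10.2.2 names the logistic treatment p-value for the week 8 endpoint. Reporting a logistic p-value beside a risk difference is common and is not in itself an error.

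**Conclusion.** The concern holds as a mismatch between the declared effect and the specified computation. Followed as coded, the analysis reports an odds ratio of about 10 where 30 percentage points is the planned effect, and the first does not determine the second. The superiority decision is not undermined; what lacks a specified estimator is the co-primary estimate and its CI.

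The comparison rests on the SAP's planning rates with no covariates or site effect; the vehicle rates other than 5% are illustrative. The week 8 Schirmer key secondary has the same gap, because SAP 10.2.2.1 refers back to 10.1.2.1.

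**What to change.** In SAP 10.1.2.1 and 15.5.1, before unblinding:

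1. In each imputed data set, predict every FAS patient's responder probability under cenegermin and under vehicle, integrating over the random site intercept (or state the alternative used).
2. Average over the FAS in each condition and take the difference.
3. Use a delta-method SE, with a bootstrap SE as the pre-specified fallback when an arm has few or no responders, and state the count that triggers it. This case is realistic: at 5%, about 2 vehicle responders are expected in 45 (45 × 0.05 = 2.25), and the chance of none is 0.95^45, about 10%. With none, the logistic fit itself may be unstable, so say there what is then reported.
4. Pool the difference and its SE by Rubin's rules.
5. Report the difference and its 95% CI as the primary effect, keep the odds ratio as supportive, and state that the one-sided p-value comes from the logistic model's treatment test.

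SAP 10.2.2.1 carries this to week 8, and the same step serves the sensitivity analysis in SAP 10.1.3. While editing the code, check the direction of the pooled difference: a comment marks TRT=2 as vehicle, but the reference level is set to 1.

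Redefining the summary as an odds ratio would also remove the contradiction, but it changes the declared estimand and would have to be listed in SAP 7.9.

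The cost is SAP wording and extra programming, with no new data and no change in sample size. One small downside is that the risk-difference CI and the logistic p-value may occasionally disagree near 0.025, which is why the SAP should say which one decides.
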